#### 18.5.1. Vital Signs Specific Derivations

Temperature (°C) = (5/9) (Temperature (°F) - 32)

#### 18.5.2. Vital Signs Markedly Abnormal Criteria

Markedly abnormal quantitative Vital Signs measurements will be identified in accordance with the following predefined markedly abnormal criteria:

Table 4: Markedly Abnormal Criteria for Vital Signs

Variable	Unit	Low	High
SBP	mmHg	≤90 mmHg	> 150 mmHg
DBP	mmHg	≤50 mmHg	> 90 mmHg
Heart rate	bpm	< 40 bpm < 50 bpm < 50 bpm and decrease from predose (Baseline) of > 10 bpm at 4 hours on Day 1 or Day 2 or remonitoring visit	> 100 bpm

bpm, beats per minute; DBP, diastolic blood pressure; SBP, systolic blood pressure.

Document: \quintiles.net\enterprise\Apps\sasdata\SASb\SAS\Arena\APD334\RZA28116\Biostatistics\Documenta

tion\SAP\503-Final SAP v2.0\APD334-203 SAP Final v2.0-20231120 clean.docx

Author: PPD Version Number: 2.0

Version Date: 20Nov2023

Template No.: CS\_TP\_BS016 Revision 7 Reference: CS\_WI\_BS005

Effective Date: 01Nov2021

Page 50 of 70

#### 18.6. Physical Examination

A listing of all physical examination assessments in participants who had at least 1 abnormal physical examination finding will be provided.

#### 18.7. Other Safety Assessments

#### 18.7.1. Pulmonary Function Test

The following pulmonary function test (PFT) measurements (actual and % Predicted) will be reported for this study:

- Forced Expiratory Volume at 1 second (FEV1)
- Forced Vital Capacity (FVC)
- Total Lung Capacity (TLC)
- FEV1/FVC
- Forced Expiratory Flow (FEF) 25-75
- Diffusing Capacity of the Lungs for Carbon Monoxide (DLCO) (if available)

The following summaries will be provided for PFT data:

- Value and change from Baseline by visit
- Incidence of markedly abnormal values by visit (Section 18.7.1.1)

All PFT data will be listed. A listing in participants who ever reported an abnormality in PFT will also be provided, including a flag for whether markedly abnormal criterion is also met.

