9.9.4. Pulmonary Function Test

Pulmonary function tests will be performed according to the Schedule of Assessments ([Table 6](#)) and includes FEV₁ and FVC measurements. All participants will have PFTs performed at Screening, and Week 12, or at the ET visit. PFTs occurring at the ET visit that are within 4 weeks of the last assessment (eg, Week 12) will only be required if clinically indicated. The 2-Week Follow-Up visit PFT assessment is only required if clinically indicated.

Participants reporting respiratory adverse events such as dyspnea during the treatment period may return at an unscheduled visit for assessment per Investigator discretion; additional PFTs may be performed as clinically indicated.

Participants experiencing a decline in PFT values (FEV₁ and/or FVC) below 50% of the predicted values must be discontinued from study treatment and scheduled for a follow-up visit.

When available, DLCO measurements will also be performed. When DLCO is not available, sites should consult the Sponsor or Sponsor's delegate. These tests will be performed at a qualified pulmonary function laboratory or respiratory department. Please refer to the American Thoracic Society/European Respiratory Society guidelines for standardization of spirometry and single breath determination of carbon monoxide uptake in the lung ([MacIntyre 2005](#), [Miller 2005a](#), [Miller 2005b](#)).

The safety of trial participants and site staff is paramount, so it is at the Investigator's discretion whether PFT can be safely administered to trial participants during the treatment period. The Investigator should evaluate on a case-by-case basis how best to proceed based on the participant's medical history, the Investigator's clinical judgment, and in consultation with the Medical Monitor. All reasonable efforts should be made to ensure safety and adherence to the protocol. When available, spirometry may be conducted at the clinical site instead of at the pulmonary laboratory. If the decision is made that it is not appropriate to conduct PFTs due to the safety concerns (eg, coronavirus disease 2019 [COVID-19] transmission), then this decision and rationale should be appropriately captured in the participant's source documentation. When available and safe (due to lifting of local restrictions, re-opening of local PFT labs, or improved safety conditions) the tests should be conducted as soon as possible and as close to the timepoints as outlined in the protocol.

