# 6.3. Retests, Unscheduled Visits and Early Termination Data

For by visit analyses and summaries, efficacy, safety, HRQoL, and biomarker data (including scheduled, retests, unscheduled, and early termination) will be assigned to visits after the application of the windowing conventions described in Section 6.4. All measurements will be considered in summaries of abnormalities or worst-case values

Document: \quintiles.net\enterprise\Apps\sasdata\SASb\SAS\Arena\APD334\RZA28116\Biostatistics\Documenta

tion\SAP\503-Final SAP v2.0\APD334-203\_SAP\_Final v2.0-20231120\_clean.docx

Author: PPD Version Number: 2.0

Version Date: 20Nov2023

Template No.: CS TP BS016 Revision 7 Reference: CS WI BS005

Effective Date: 01Nov2021

Page 22 of 70

post-Baseline.

The visit windowing will be applied before missing data are imputed.

Listings will include scheduled, unscheduled, retest, and early termination data.

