If one or more results for a variable are assigned to the same analysis visit, the result with the date closest to the protocol scheduled day will be used in the analysis, except for component subscores of MMS or TMS, in which case, the composite score and component subscores from the same date will be used in the analysis. If two measurements in the same analysis visit window are equidistant from the protocol scheduled study day, the earliest measurement will be used in the analysis. If multiple assessments are available on the same day, then the average of the assessment will be used in the analysis, except for laboratory and ECG data where the assessment at the earliest time of the same day will be used. If both central and local assessments of the same ECG or lab test are available on the same day/analysis visit, the central result will take precedence over the local result.

Document: \quintiles.net\enterprise\Apps\sasdata\SASb\SAS\Arena\APD334\RZA28116\Biostatistics\Documenta

tion\SAP\503-Final SAP v2.0\APD334-203\_SAP\_Final v2.0-20231120\_clean.docx

Author: PPD Version Number: 2.0

Version Date: 20Nov2023

Template No.: CS\_TP\_BS016 Revision 7 Reference: CS\_WI\_BS005

Effective Date: 01Nov2021

Page 23 of 70

For the overlapping visit windows at Week 12 and Week 8, a hierarchical algorithm will be applied as following: always map to the Week 12 study visit if the study day falls within the visit window of the Week 12 study visit, then assess the other records for the Week 8 study visit.

Table 2: Visit Windows for Efficacy and Safety Analyses

For All Efficacy (Except Endoscopy/MMS/Histology), Efficacy-Related Biomarkers, Safety Labs and Vital Signs			
Scheduled Study Visit (Protocol Scheduled Day)	Analysis Visit Window (Study Day)		
Baseline	≤1		
Week 0 (Day 1)	1		
Week 0 (Day 2)a	2		
Week 2 (Day 15 ± 3)	2 to 22, or 3 to 22a		
Week 4 (Day 29 ± 3)	23 to 43		
Week 8 (Day 57 ± 3)	44 to 71		
Week 12 (Day 85 ± 7)	> 71		
	gy/All Composite Endpoints That Include an Endoscopy Component sysician's Global Assessment, Health-Related Quality of Life, ECGs, OCT,		
Scheduled Study Visit (Protocol Scheduled Day)	Analysis Visit Window (Study Day)		
Baseline	≤1		
Week 0 (Day 1)	1		
Week 0 (Day 2)a	2		
Week 12 (Day 85 ± 7)b,c	66 to 113e (66 to 141 for assessments impacted by COVID-19 pandemic)d		
	or 57 to 113 f (57 to 141 for assessments impacted by COVID-19 pandemic) e		

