# 7. DETERMINATION OF SAMPLE SIZE

Based on a Chi square test at 2-sided significance level of 0.05, a total of 96 participants (32 per treatment group) will provide at least 80% power to show pairwise superiority of etrasimod 2 mg to placebo in the primary endpoint assuming 5% remission rate in the placebo group and a 31.5% remission rate in the etrasimod 2 mg group. The assumptions are based on the results from the completed Phase 2 Study APD334-003. Sample size is calculated using the EAST® software.

The actual sample size will be smaller than original planned because this study will be early discontinued in agreement with PMDA consultation.

Document: \quintiles.net\enterprise\Apps\sasdata\SASb\SAS\Arena\APD334\RZA28116\Biostatistics\Documenta

tion\SAP\503-Final SAP v2.0\APD334-203\_SAP\_Final v2.0-20231120\_clean.docx

Author: PPD Version Number: 2.0

Version Date: 20Nov2023

Template No.: CS\_TP\_BS016 Revision 7 Reference: CS\_WI\_BS005

Effective Date: 01Nov2021

<sup>e Not applicable for OCT/PFT

f Applicable for OCT/PFT

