#### 18.4. ECG Evaluations

Electrocardiograms (ECG) are recorded on a 12-lead ECG machine and read centrally. The following ECG parameters will be reported for this study:

- HR (beats per minute [bpm])
- PR interval (ms)
- RR interval (ms)
- QRS interval (ms)
- QT interval (ms)
- QTcF interval (ms)
- Overall interpretation of ECG (Investigator's judgment):
  - Normal
  - Abnormal, Not Clinically Significant (Abnormal not clinically significant [NCS])
  - Abnormal, Clinically Significant (Abnormal CS)
- Overall interpretation of ECG (central reader):
  - Normal

Document: \quintiles.net\enterprise\Apps\sasdata\SASb\SAS\Arena\APD334\RZA28116\Biostatistics\Documenta

tion\SAP\503-Final SAP v2.0\APD334-203\_SAP\_Final v2.0-20231120\_clean.docx

Author: PPD Version Number: 2.0

Version Date: 20Nov2023

Template No.: CS\_TP\_BS016 Revision 7 Reference: CS\_WI\_BS005

Effective Date: 01Nov2021

Page 47 of 70

- Abnormal NCS
- Abnormal CS
- AV conduction abnormalities
  - First degree AV block
  - Second degree AV block type 1
  - Second degree AV block type 2
  - Third-degree AV block

The following summaries will be provided for ECG data:

- Value and change from Baseline by visit (for quantitative measurements)
- Incidence of markedly abnormal values (defined in Section 18.4.1) and AV blocks by visit
- Shift in normal/abnormal NCS/abnormal CS in the overall interpretation (by investigator) from Baseline to end
  of treatment and to the worst-case post-Baseline
- Shift in markedly abnormal categories from Baseline to post-Baseline by visit

Listings of ECG results, including first dose cardiac monitoring, and discharge criteria for first dose cardiac monitoring will be provided.

A listing of all ECG assessments over time in participants meeting markedly abnormal criteria will also be provided. For each subject, only ECG parameters ever meeting markedly abnormal criteria will be included.

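### SAP Table 2 gives mid-treatment OCT, PFT and ECG results no analysis visit, so the by-visit safety tables have no row for abnormalities that SAP 6.3 says are to be considered

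*SAP*

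**What the plan says.** SAP 6.3 sets two rules. For by-visit summaries, data of every kind, including retests, unscheduled and ET results, "will be assigned to visits after the application of the windowing conventions described in Section 6.4". For abnormalities after Baseline, "All measurements will be considered in summaries of abnormalities or worst-case values".

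SAP 6.4, Table 2, has two panels. The panel for vital signs and safety laboratory tests runs without a break from Day 2 onward. The panel that holds ECG and OCT has only Baseline, Day 1, Day 2 and Week 12. Its Week 12 window is "66 to 113e (66 to 141 for assessments impacted by COVID-19 pandemic)d", which footnote e marks as not for OCT/PFT. The alternative window is Day 57 to 113 ("57 to 141 for assessments impacted by COVID-19 pandemic"), marked "f Applicable for OCT/PFT". Footnote a restricts the Day 2 row to vital signs and ECGs under extended monitoring.

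The outputs follow the visits. PFT has "Incidence of markedly abnormal values by visit (Section 18.7.1.1", OCT has categorical results by visit, and ECG has "Incidence of markedly abnormal values (defined in Section 18.4.1) and AV blocks by visit".

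Protocol 9.9.4 says that participants whose FEV1 and/or FVC declines "below 50% of the predicted values must be discontinued from study treatment and scheduled for a follow-up visit". Protocol 5.1 also makes confirmed, clinically significant macular edema a mandatory stop.

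**The concern.** A participant who stops treatment early has the ET visit within 7 days of the last dose (Protocol 5.1), and Protocol Table 6 places ECG, PFT and OCT at that visit. Symptom-driven tests are allowed at other times (Protocol 9.9.3 to 9.9.5). The windows therefore have to take in results from the middle of the treatment period, and for these three tests they do not.

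The SAP's markedly abnormal cut-offs for FEV1 and FVC (18.7.1.1) are the same 50% of predicted that forces a stop. The table that counts such values may thus have no row for the value that ended a participant's treatment. SAP 6.6 defines a proportion at a visit over the participants at that visit. Someone tested only in the gap would then be missing from both numerator and denominator, and the Week 12 column would describe those tested from Day 57 (OCT/PFT) or Day 66 (ECG) onward.

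**Working it through.** No planned figure is at issue. The check sets Study Days 1 to 85 (Week 12 is scheduled for Day 85) against the Table 2 windows.

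**Inputs**
- OCT/PFT: Baseline (Day 1 or earlier), Day 1, and Week 12 from Day 57 (footnote f). There is no Day 2 row (footnote a). The panel heading is cut off after OCT in the text available, so PFT membership is taken from footnotes e and f.
- ECG: Baseline, Day 1, Day 2 (extended monitoring) and Week 12 from Day 66.
- Vital signs and safety laboratory tests: Days 2 to 22, 23 to 43, 44 to 71, and after 71. With extended monitoring, Day 2 has its own row and the Week 2 window starts on Day 3.

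**Days with no analysis visit**

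| Test | Uncovered days | Count | Share of Days 1 to 85 |
|---|---|---|---|
| OCT/PFT | 2 to 56 | 56 − 2 + 1 = 55 | 55/85 = 64.7% |
| ECG (Day 2 row taken as available) | 3 to 65 | 65 − 3 + 1 = 63 | 63/85 = 74.1% |
| Vital signs, laboratory | none | 0 | 0% |

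The shares describe the calendar, not the data.

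**Two examples.** An ET PFT on Day 60 with FEV1 below 50% predicted falls within Day 57 to 113 and is counted at Week 12. The same result on Day 40 is after Day 1 and before Day 57, so it has no visit. SAP Appendix 1 does not help, because it makes the period for ET data depend on the analysis visit assigned under 6.4.

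**Other routes by which a gap result could be counted**
- *Cardiac Remonitoring visits (SAP 6.4)* take ECGs done on re-initiation after an interruption, but not other ECGs on Days 3 to 65.
- *Follow-up visits* are summarized separately without windows. The 2-Week Follow-Up PFT and OCT are required only if clinically indicated, so they do not replace the ET test.
- *ECG worst-case shift (SAP 18.4)* covers the investigator's overall interpretation, but not the QT/QTcF criteria or AV blocks.
- *Any-time row:* SAP 18.3.1 has one for low lymphocytes and neutrophils. Sections 18.7.1 and 18.7.2 have none, and 18.4 has none for markedly abnormal values or AV blocks.

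The second rule of 6.3 therefore brings these results in, while Table 2 and the by-visit outputs give them no place.

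**The case against.** The strongest reply is that SAP 6.3 already settles the matter. Incidence of markedly abnormal PFT values is a summary of abnormalities, so all measurements count, and the layout is left to output shells that are not in the documents. This is partly right: no rule expressly discards the values. But the SAP text commits only to by-visit incidence, and a programmer following Table 2 must either leave the value out or add a row that the plan does not specify.

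The second reply is that little is hidden, and this stands. All PFT, OCT and ECG results are listed, with further listings of participants who had an abnormality. Events reported as TEAEs are counted without visit windows in the adverse event, special-interest and discontinuation tables (SAP 18.1). SAP 18.1.5 also provides for a review of test data to find special-interest cases that investigators missed.

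Three stronger readings are tempting, and the documents do not support them.
- *The special-interest event tables understate risk.* Those tables are built from TEAEs, not from windowed test results.
- *ECG findings that force a stop are lost.* The ECG-related mandatory stops in Protocol 5.1 belong to Day 1 and Day 2 monitoring, and ECG has analysis visits on both days. A confirmed new QTc above 500 ms at any time in the treatment period requires interruption (Protocol 9.9.3), which is a different rule.
- *The loss falls on the active arms only.* Protocol 3.2 reports TEAE discontinuations in the earlier Phase 2 study of 5.8% (1 mg), 8.0% (2 mg) and 0% (placebo). At 32 per arm that would be 32 × 0.058 = 1.9, 32 × 0.080 = 2.6 and 0. Those rates cover TEAEs of every kind, give no timing, and are not tied to any PFT, OCT or ECG finding. The actual sample will be smaller than planned (SAP 7). Placebo participants who leave for lack of efficacy or withdrawal have ET visits too, and those can fall in the same gap.

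**Conclusion.** The point holds, within limits. The windows leave OCT/PFT results on Days 2 to 56 without a row in the tables of 18.7.1 and 18.7.2. ECG results on Days 3 to 65 outside remonitoring likewise have no row in the markedly abnormal and AV block summary of 18.4. For PFT and OCT this includes results that trigger a mandatory stop. It is an unreconciled conflict with SAP 6.3, confined to by-visit tables based on test results.

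Its size cannot be determined from the documents. They do not give the number of ET or unscheduled tests in the gap, their timing, or their split by arm. A reader might take 65% and 74% as the share of data lost. They are not: no PFT or OCT is routinely scheduled on Days 2 to 56, and no ECG on Days 3 to 65 apart from ET. No efficacy endpoint is affected. The correction is still worth making, because the study is stopping early and is descriptive (SAP 3.3), so one uncounted case can change a small table.

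The conclusion assumes that PFT shares the OCT panel, as the footnotes indicate, and that the shells add no row beyond the SAP text.

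**What to change.** Add a row for any time post-Baseline, using the worst value and including unscheduled and ET results, with the Safety Set as denominator, to three summaries:
- PFT markedly abnormal values, and the potentially important criteria (SAP 18.7.1 and 18.7.1.1)
- OCT categorical results (SAP 18.7.2)
- ECG markedly abnormal values and AV blocks (SAP 18.4)

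State in SAP 6.4 that OCT, PFT and ECG results outside the Week 12 window feed this row, in line with 6.3. The by-visit rows can stay as they are. The cost is that wording and one row in three table shells. No new data are needed and study conduct does not change.

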#### 18.7.1.1. PFT MARKEDLY ABNORMAL AND POTENTIALLY IMPORTANT CRITERIA

Markedly abnormal quantitative PFT measurements will be identified in accordance with the following predefined markedly abnormal criteria:

- % Predicted FEV1 < 50%

- % Predicted FVC < 50%

- % Predicted FEV1/FVC ratio < 50%

Potentially important PFT measurements will also be identified using the criteria below:

Document: \quintiles.net\enterprise\Apps\sasdata\SASb\SAS\Arena\APD334\RZA28116\Biostatistics\Documenta

tion\SAP\503-Final SAP v2.0\APD334-203\_SAP\_Final v2.0-20231120\_clean.docx

Author: PPD Version Number: 2.0

Version Date: 20Nov2023

Template No.: CS\_TP\_BS016 Revision 7 Reference: CS\_WI\_BS005

Effective Date: 01Nov2021

Page 51 of 70

- Decrease from Baseline > 20% in FEV1, ie, percent change from Baseline < -20%

- Decrease from Baseline > 20% in FVC, ie, percent change from Baseline < -20%

- Decrease from Baseline > 20% in DLCO, ie, percent change from Baseline < -20%

#### 18.7.2. Ophthalmoscopy and Optical Coherence Tomography

The following summaries will be provided for ophthalmoscopy and optical coherence tomography (OCT) data:

- Values and change from Baseline in intraocular pressure by visit
- Categorical result in ophthalmoscopy with OCT parameters by visit (the categories are listed on the Ophthalmoscopy with OCT eCRF)

A listing of all ophthalmoscopy and OCT assessments will be provided. A listing of participants who ever reported an abnormality in OCT will also be provided. Additionally, a listing of retinal photograph and eye pressure assessments will be provided for participants who experienced an AE related to eye disorders.

#### 18.7.3. Tuberculosis Screening and Chest X-Ray

Screening tuberculosis results and chest X-rays will be listed. Results of tuberculosis questionnaires will also be listed.

#### 19. PHARMACOKINETIC ANALYSIS

Plasma concentrations of etrasimod will be assessed from samples collected prior to dosing and 4 hours (±15 minutes) post-dose (after 12-lead ECG) on Week 0/Day 1, samples collected prior to dosing (trough; within 60 minutes prior to dosing) at Weeks 2, 4, 8, and 12. Additionally, samples are being collected at 2-Week and 4-Week Safety Follow-up visits (for subjects not enrolling into the OLE study), and if possible, at the time of any SAE or adverse event leading to study treatment discontinuation are being collected. Concentrations below the limit of quantification (BLQ) will be assigned a numerical value of zero for the calculation of descriptive statistics in concentrations (except for geometric mean and geometric %CV) and plotting of concentrations. For geometric mean and geometric %CV, the zero values will be excluded.

The pharmacokineticist will determine the strategy for dealing with data affected by protocol deviations or events which may impact the quality of PK concentration data on a case-by-case basis with input from the Pfizer study physician and Pfizer clinical pharmacologist, as needed. Examples for protocol deviations or events include, but

Document: \\quintiles.net\enterprise\Apps\sasdata\SASb\SAS\Arena\APD334\RZA28116\Biostatistics\Documenta

tion\SAP\503-Final SAP v2.0\APD334-203 SAP Final v2.0-20231120 clean.docx

Author: PPD Version Number: 2.0

Version Date: 20Nov2023

Template No.: CS\_TP\_BS016 Revision 7 Reference: CS\_WI\_BS005

\_\_\_\_\_

Effective Date: 01Nov2021

Page 52 of 70

may not be limited to, vomiting on the day prior to trough sample collection, sample processing errors that lead to inaccurate bioanalytical results, and/or inaccurate dosing prior to PK sampling. In the case of an important protocol deviation or event, the affected PK data collected may be excluded from the summaries, calculation of the average steady state trough plasma concentration ( $C_{trough}$ ) based on available Week 2 to Week 12 trough concentrations ( $C_{trough,ss,W2-W12}$ ), exposure-response analysis, and/or population PK analysis, but will still be reported in the study result listings. The time window of 24 hours ±8 hours after the last dose prior to PK sample is required for inclusion in calculating  $C_{trough,ss,W2-W12}$  and summarizing trough.

Unless otherwise specified, PK summaries will use the Pharmacokinetic Set. Exposure-response analysis will use the Safety Set.

Individual subject etrasimod plasma concentrations will be presented in the data listings, including subject ID, treatment received, sex, age, weight, nominal timepoint, actual blood collection date/time, concentration, and time since last dose, and also summarized using descriptive statistics (n, mean, SD, %CV, geometric mean, geometric % CV, median, minimum, and maximum) by nominal timepoint and treatment. Summary table will be repeated by: Sex (male/female), age at consent (<18, 18 to <65, ≥65), Tobacco use (Yes/No), and weight (≤ Median or > Median).

All subjects are expected to achieve steady-state plasma concentration by Week 2. For each subject, the average steady state trough (pre-dose) plasma concentration (Ctrough) based on Week 2 to Week 12 trough concentrations (Ctrough,ss,W2-W12) per subject will also be calculated and presented in a data listing and summarized using descriptive statistics by treatment.

Mean ( $\pm$ SD) etrasimod concentration versus nominal time will be plotted by treatment on linear scale. Summary figure will be repeated by: Sex (male/female), age at consent (<18, 18 to <65,  $\geq$ 65), Tobacco use (Yes/No), and weight ( $\leq$  Median or > Median).

Box plots of etrasimod concentrations at Day 1, 4 hour post-dose timepoint (C4hr) and average steady-state  $C_{trough}$  (Weeks 2 through 12 [ $C_{trough,ss,W2-W12}$ ]) will be plotted versus nominal timepoint on ordinal scale, separately by treatment. Box plots figure will be repeated by: Sex (male/female), age at consent (<18, 18 to <65,  $\geq$ 65), Tobacco use (Yes/No), and weight ( $\leq$  Median or > Median).

Individual subject plasma concentrations versus actual time will be plotted since start of treatment on linear scale.

Scatter plots of individual subject average steady-state Ctrough ss,W2-W12 versus Baseline body weight and versus Baseline age as continuous variables will be generated by treatment for the Pharmacokinetic Set, which will also include the Spearman's rank correlation coefficient, p-value, and LOESS trend line.

Document: \quintiles.net\enterprise\Apps\sasdata\SASb\SAS\Arena\APD334\RZA28116\Biostatistics\Documenta

tion\SAP\503-Final SAP v2.0\APD334-203 SAP Final v2.0-20231120 clean.docx

Author: PPD Version Number: 2.0

Version Date: 20Nov2023

Template No.: CS\_TP\_BS016 Revision 7 Reference: CS\_WI\_BS005

Effective Date: 01Nov2021

Page 53 of 70

To explore potential etrasimod plasma exposure-response relationships, the following scatter plots will be generated in the Safety Set, including data from placebo subjects (plotted at 'zero' concentration). Any contributing data from the placebo subjects will be annotated with a different color or symbol. All scatter plots will include the Spearman's rank correlation coefficient, p-value, and LOESS trend line (based on subjects that received active treatment only).

- Individual subject absolute change from Baseline in MMS versus etrasimod steady state Ctrough at
  the common visit where both MMS and Ctrough are measured (Week 12). Figure will be repeated
  by: Sex (male/female), age at consent (<18, 18 to <65, ≥65), Tobacco use (Yes/No), and weight (≤
  Median or > Median).
- Individual subject absolute change from Baseline in MMS versus average steady-state Ctrough ss,W2-W12. Figure will be repeated by: Sex (male/female), age at consent (<18, 18 to <65, ≥65), Tobacco use (Yes/No), and weight (≤ Median or > Median).
- Individual subject lymphocytes versus etrasimod steady-state Ctrough by Visit (Week 2 to Week
   12). Figure will be repeated by: Sex (male/female), and age at consent (<18, 18 to <65, ≥65).

- Individual subject absolute changes from Baseline in lymphocytes versus etrasimod steady-state
   Ctrough by Visit (Week 2 to Week 12). Figure will be repeated by: Sex (male/female), and age at
   consent (<18, 18 to <65, ≥65).

- Individual subject percent changes from Baseline in lymphocytes versus etrasimod steady-state
   Ctrough by Visit (Week 2 to Week 12). Figure will be repeated by: Sex (male/female), and age at
   consent (<18, 18 to <65, ≥65).

Furthermore, the following overlay plots will be generated in the Pharmacokinetic Set within the etrasimod group only:

- Mean (SD) absolute lymphocytes and mean (SD) etrasimod concentration versus nominal timepoint (Weeks 0 through 12). This figure will be repeated by: Sex (male/female), and age at consent (<18, 18 to <65, ≥65).

- Mean (SD) absolute change from Baseline in lymphocytes and mean (SD) etrasimod concentration versus nominal timepoint (Weeks 0 through 12). This figure will be repeated by: Sex (male/female), and age at consent (<18, 18 to <65, ≥65).

- Mean (SD) percent change from Baseline in lymphocytes and mean (SD) etrasimod concentration versus nominal timepoint (Weeks 0 through 12). This figure will be repeated by: Sex (male/female), and age at consent (<18, 18 to <65, ≥65).

- Mean (SD) heart rate and mean (SD) etrasimod concentration versus nominal timepoint (Weeks 0 through 12).
   This figure will be repeated by: Sex (male/female), and age at consent (<18, 18 to <65, ≥65).

- Mean (SD) absolute change from Baseline in heart rate and mean (SD) etrasimod concentration versus nominal

Document: \quintiles.net\enterprise\Apps\sasdata\SASb\SAS\Arena\APD334\RZA28116\Biostatistics\Documenta tion\SAP\503-Final SAP v2.0\APD334-203 SAP Final v2.0-20231120 clean.docx

Author: PPD Version Number:

Version Date: 20Nov2023

2.0

Template No.: CS\_TP\_BS016 Revision 7 Reference: CS\_WI\_BS005

Effective Date: 01Nov2021

Page 54 of 70

timepoint (Weeks 0 through 12). This figure will be repeated by: Sex (male/female), and age at consent (<18, 18 to <65,  $\geq$ 65).

